#### **9.5.1.2 Sensitivity Analysis**

The following sensitivity analyses will be conducted using the same M-H method as in primary analysis:

- PCAS: similar to primary analysis method but only subjects who meet the criteria for inclusion in the PCAS are included.
- LVCF: similar as primary analysis method but using LVCF to impute missing data during the EAP. For subjects without PTH data during the EAP, the mean of the last 2 pre-dialysis PTH values obtained after Study Day 1 will be carried forward. If only one value is available, this single value will be carried forward to the EAP. The same imputation strategy for primary analysis will be employed for subjects without a post baseline PTH value.
- PPAS: similar as primary analysis method but only the subjects who meet the criteria for inclusion in the PPAS are included.

#### **9.5.2 Analyses of Secondary Efficacy Endpoint(s)**

Sequential testing of the following two key secondary efficacy endpoints will be performed in this order if non-inferiority is demonstrated on the primary endpoint.

- achievement of > 50% reduction in mean predialysis serum PTH during the EAP from baseline (superiority)
- achievement of > 30% reduction in mean predialysis serum PTH during the EAP from baseline (superiority)

#### **9.5.2.1 Primary Analysis**

The endpoint of achievement of > 50% reduction in mean predialysis serum PTH during the EAP from baseline will be analyzed using the CMH test stratified by the randomization stratification factors and based on the FAS. The non-responder

imputation strategy will be used for subjects with no PTH value during the EAP. The endpoint of achievement of > 30% reduction in mean pre-dialysis serum PTH during the EAP from baseline for superiority will be analyzed similarly using CMH test with non-responder imputation strategy applied for subjects who have no PTH value during EAP. Subgroup analysis for both endpoints will be performed based on baseline covariates listed in [Section 4.1](#).

#### **9.5.2.2 Sensitivity Analysis**

The sensitivity analysis for the key secondary endpoint of proportion of subjects who have achievement of > 50% reduction from baseline in mean pre-dialysis serum PTH during EAP will be performed based on the FAS. The multiple imputation method will be used to carry out the multiple imputation using SAS® PROC MI. The Fully Conditional Specification (FCS) method (SAS/STAT® 9.3 User's Guide) will be used to carry out the multiple imputation using SAS® PROC MI. PTH values from all post Study Day 1 scheduled visits will be included in the imputation model. The mean PTH value over the EAP is treated as a single time point. Treatment group, stratification factors, baseline covariates (as detailed in [Section 4.1](#)), will be considered for inclusion in the model as auxiliary variables. With FCS method, the missing PTH values are imputed sequentially in the order specified in the VAR statement (chronological order). Each imputed dataset will be analyzed using stratified CMH method. Final result of CMH estimate and odds ratio are based on combined inference from each of the imputed datasets.

The same sensitivity analyses will be repeated for the key secondary endpoint of proportion of subjects who have achievement of > 30% reduction from baseline in mean pre-dialysis serum PTH during EAP for superiority in the same manner with the same group of auxiliary variables when imputing the mean of PTH value over the EAP. Each imputed dataset will be analyzed using stratified CMH method. Final result of CMH estimate and odds ratio are based on combined inference from each of the imputed datasets.

[figure not shown]
The following other secondary endpoints will be evaluated for superiority if the above key secondary endpoints are considered statistically significant. To control the experiment-wise error rate, the Hochberg procedure of adjustment for multiple comparisons will be used for the following:

- percent change from baseline in mean pre-dialysis measured by central laboratory serum cCa during the EAP
- achievement of mean pre-dialysis serum P ≤ 4.5 mg/dL during the EAP

A repeated measures mixed effects model will be used to compare treatment groups with respect to the percent change from baseline in serum cCa levels during the EAP, and will include the treatment group, randomization stratification factors, study week and study week by treatment as fixed effects. The difference of least square means between treatment groups will be presented with 95% CI. The FAS will be used for these analyses, and cCa completer set will be used for sensitivity analysis. Only central laboratory measured cCa will be used.

The secondary endpoint of proportion of subjects with mean pre-dialysis measured by central laboratory  $P \leq 4.5$  mg/dL during the EAP will be analyzed using the CMH test stratified by the randomization stratification factors. The difference between treatments will be estimated and presented with a 95% confidence interval. These analyses will be performed on the FAS using the non-responder method of imputation for those subjects without laboratory values during the EAP. The mean pre-dialysis  $P$  will be derived based on all central laboratory measured of  $P$  during EAP.

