### Efficacy Assessment Phase (EAP)

The period between Week 20 and Week 27, inclusive.

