### Baseline Values

Baseline values of PTH, cCa, and serum phosphorus are defined as the average of the last pre-dialysis assessment done during the screening period and the pre-dialysis assessment done on Study Day 1.

All other baseline laboratory values are using the last non-missing assessment taken prior to or on Study Day 1 (Study Day 1 assessment if available, otherwise the last screening assessment prior to Study Day 1).

Baseline vital sign and weight will be the last post-dialysis assessment values prior to or on Study Day 1.

The use of vitamin D, including nutritional vitamin D (vitamin D supplement) and vitamin D sterol (active vitamin D), is defined as use of vitamin D during the 7 days period prior to Study Day 1, inclusive.

The use of other concomitant medication of interest at baseline is defined as use of each concomitant medication on Study Day 1. This includes medication use that starts prior to Study Day 1 and ends on Study Day 1 or duration of use covers Study Day 1.

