### **5.3 Other Study Related Definitions**

#### Protocol Scheduled Visits

The clinical planned event (CPE) assigned in the clinical database will be used as protocol scheduled visits. If the value at a scheduled visit is missing, an unscheduled assessment can be used provided the unscheduled assessment occurs within the window for that study week, ie

$$\text{ceiling}(\text{study day of the unscheduled visit} / 7) = \text{study week number}$$

All missing scheduled assessments will be replaced using the above method, if possible, prior to deriving any study endpoints.

If the value at a scheduled visit is missing and multiple unscheduled assessments occurs within the window of this visit, or there are multiple values at a scheduled visit, then the first record will be used for the visit.

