#### Mean Value of Efficacy Endpoints during the EAP

The mean of the scheduled (including the missing scheduled assessments replaced by unscheduled assessments as described above) pre-dialysis assessments taken during week 20 to week 27, inclusive.

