#### **6.5 cCa Completer Analysis Set**

The cCa Completer Analysis Set (CCAS) includes all randomized subjects with at least one predialysis cCa value, measured by the central laboratory, during the EAP. Subjects will be analyzed according to randomized treatment group.

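### The completer-set sensitivity run for percent change in cCa uses the same rows as the main EAP-only model, so it must return the same result; the model also leaves out continuous baseline cCa

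*SAP*

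**What the plan says.** SAP 9.5.2.2 fits a repeated measures mixed model to percent change in serum cCa over the EAP, using central-laboratory values only. The model "will include the treatment group, randomization stratification factors, study week and study week by treatment as fixed effects". On analysis sets it says: "The FAS will be used for these analyses, and cCa completer set will be used for sensitivity analysis". Protocol 10.5.3.1 plans the same pair of runs but calls the completer run supplementary.

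The definitions that matter are these:

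- **EAP** (SAP 5.1): "The period between Week 20 and Week 27, inclusive". The EAP mean in SAP 5.3 likewise covers "pre-dialysis assessments taken during week 20 to week 27, inclusive". Protocol Table 3 schedules albumin and calcium in that window at weeks 20, 22, 24, 26 and 27.
- **cCa Completer Analysis Set, CCAS** (SAP 6.5): it "includes all randomized subjects with at least one predialysis cCa value, measured by the central laboratory, during the EAP".
- **Replacement of missing visits** (SAP 5.3): "an unscheduled assessment can be used provided the unscheduled assessment occurs within the window for that study week".
- **Missing laboratory values**: SAP 8.3 refers to 9.5.1 and 9.5.2. Those sections give rules for PTH and phosphorus, and none for cCa.
- **Baseline** (SAP 5.2): "Baseline values of PTH, cCa, and serum phosphorus are defined as the average of the last pre-dialysis assessment done during the screening period" and the day 1 value. It is the denominator of the percent change. The only cCa adjustment in the model is the stratification factor, screening cCa split at 9.0 mg/dL.

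**The concern.** A sensitivity analysis is useful only if it could come out differently from the main analysis. Here both runs appear to use the same rows. The agreement would be automatic, yet a study report could present it as evidence of robustness to missing data.

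The endpoint is formally tested for superiority under the Hochberg procedure (SAP 9.1), and no other planned analysis fills the gap. SAP 8.4 promises to explore dropout only if it differs between arms, and names no method. SAP 9.6.3 gives descriptive summaries by visit, which do not check the tested contrast. SAP 8.6 checks normality.

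The second point is smaller. The endpoint divides by baseline cCa, so it will often correlate with baseline, but the model adjusts only for a two-level screening version of it. That can waste precision.

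**Working it through.** The documents give no effect size, SD or power for this endpoint, so there is no planned figure to reproduce.

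**1. Identity of the two runs**

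- A likelihood mixed model uses only subject-week rows with an observed outcome.
- With EAP weeks only, a randomized subject has a row if and only if at least one central cCa exists in weeks 20 to 27.
- That is the CCAS membership rule. Every subject with a row is in the CCAS, and every FAS subject outside it has none.
- Same-week replacement changes nothing, because a subject with no EAP value still has no row.

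The estimate, SE, confidence interval and p-value therefore agree under any covariance structure. Two simulated trials of 660 subjects (REML, random intercept, SAP fixed effects) confirm this:

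- With 66 subjects lacking EAP cCa (CCAS 594), the largest difference in any coefficient or SE was 0.0.
- With 80 lacking it (CCAS 580), both runs gave -2.31875 (SE 0.42856) from the same 2746 rows.

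**2. What happens if earlier weeks are modelled**

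In the second data set, all post-baseline weeks with an EAP-averaged contrast gave:

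- FAS: -2.263 (SE 0.402; 660 subjects, 8149 rows)
- CCAS: -2.321 (SE 0.423; 580 subjects, 7706 rows)

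The runs now differ, so the identity depends on which weeks enter.

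**3. What the missing records could hide**

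The documents' only figure is 10% dropout (Protocol 10.2, SAP 3.2). *Assumption:* it applies to EAP cCa, so 0.10 × 330 = 33 per arm (66 of 660) have no record, leaving 297 per arm. If the unobserved subjects in one arm differ from its observed subjects by δ points, that arm's full mean is observed + 0.10 × δ, and the contrast moves by 0.10 × δ.

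SE = SD × √(2/297) = SD × 0.0821. This is 0.49 for an SD of 6 points and 0.82 for an SD of 10 (both assumed).

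| δ (points) | Shift in contrast | In SE, SD 6 | In SE, SD 10 |
|---|---|---|---|
| 1 | 0.1 | 0.2 | 0.1 |
| 3 | 0.3 | 0.6 | 0.4 |
| 5 | 0.5 | 1.0 | 0.6 |

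**4. Baseline covariate**

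All inputs are assumed:

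- screening and day-1 cCa correlation 0.75, with baseline as their mean (SD 0.55 mg/dL);
- subjects with screening cCa of at least 8.3 retained, and EAP mean 3% lower than baseline;
- 1,000,000 simulated subjects per setting.

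The entries are the excess SE: the residual SD with only the screening < 9.0 indicator, relative to that with continuous baseline cCa added. The three figures in each cell are for baseline-EAP correlations 0.3 / 0.5 / 0.7.

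| Mean cCa (mg/dL) | EAP/baseline SD ratio 1.0 | 1.2 | 1.4 |
|---|---|---|---|
| 9.0 | 7.4 / 4.5 / 2.2% | 4.3 / 2.0 / 0.4% | 2.6 / 0.8 / 0.0% |
| 9.2 | 9.0 / 5.5 / 2.7% | 5.2 / 2.4 / 0.5% | 3.2 / 1.0 / 0.0% |
| 9.6 | 13.2 / 8.2 / 4.0% | 7.8 / 3.5 / 0.6% | 4.8 / 1.4 / 0.0% |

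Varying baseline SD over 0.45 to 0.65 widens the whole range to 0-15%.

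A separate check in the repeated-measures model, with assumed slopes of 0, -2.5, -5 and -7.5 percentage points per mg/dL, gave SE ratios (without / with baseline) of 1.00, 1.01, 1.07 and 1.16.

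Bias was checked with 3000 simulated trials and a true effect of -2.00. With dropout unrelated to baseline, both models gave -2.00. With dropout made to depend on baseline cCa in one arm only, the model without baseline gave -2.16 and the model with it gave -2.00.

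**The case against.** The strongest objection is that the SAP never states which study weeks enter the model. If pre-EAP weeks were meant, the runs differ, and naming two runs suggests the authors expected them to. The EAP-mean definition is also weak support for the EAP-only reading, because a model with study week as a term does not use that mean.

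This stands as a condition on the identity. EAP-only is still the more natural reading: both documents describe the modelled outcome as change during the EAP. For the PTH imputation the same SAP section names earlier visits outright ("PTH values from all post Study Day 1 scheduled visits will be included in the imputation model"), though that is a different variable and method. If earlier weeks were intended, the text is still incomplete, because it asks for a difference of least squares means without restricting it to weeks 20 to 27. An edit is needed on either reading.

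A second objection is that 10% overstates the missing share. It is a sample-size allowance. Protocol 6.2.3 continues assessments during dose suspension, subjects off treatment may stay in follow-up, and someone leaving after week 20 may have an EAP value. This stands, and the share with no EAP cCa may well be lower. However, Protocol 8.3.1 requires only vital status at week 26 after removal from treatment, so missing EAP cCa remains realistic.

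A third objection is that the baseline covariate is a matter of preference: the planned analysis is valid, every precision input is assumed, and the gain can be nil. This largely stands. The covariate is recommended because it is already collected and costs almost nothing.

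**Conclusion.** The concern holds, as a minor point. If only EAP weeks are modelled, the CCAS run must reproduce the FAS result exactly, whether it is called sensitivity or supplementary. A formally tested endpoint is then left without any specified check on missing data. The identity is algebraic. The possible shift of 0.10 points per 1-point difference is an illustration resting on the 10% assumption, not a prediction.

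Leaving out continuous baseline cCa does not invalidate the analysis. The cost is precision, possibly negligible, provided EAP missingness does not depend on baseline cCa differently by arm.

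The consequences are limited. The endpoint is tested only after the primary and both key secondary tests succeed.

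**What to change.** Before unblinding:

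1. State which study weeks enter the cCa model, and define the tested contrast as the treatment difference averaged over weeks 20 to 27.
2. Choose one of two routes:
   - Include all scheduled post-baseline central cCa visits and estimate the EAP contrast. The CCAS run can then differ, although a completer subset still does not test missingness that depends on unobserved values. In the simulated example the gap was 2.321 - 2.263 = 0.058 points, about 0.14 SE.
   - Keep EAP weeks only, say so, and replace the CCAS run with an analysis that can differ. The multiple imputation already specified for PTH in SAP 9.5.2.2 could be applied to cCa, with a range of shifts applied to the imputed values. This is the option that probes departures from missingness at random.
3. Add continuous baseline cCa and its interaction with week to the fixed effects.
4. Record any departure from Protocol 10.5.3.1 in SAP Section 10, which currently declares none.

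The cost is SAP wording and model code; no new data are needed. The downsides are a longer model specification and a declared addition to the protocol's analysis. The all-visit model and the unshifted imputation both rely on missingness at random given earlier cCa.

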1.2 Secondary

- To assess whether treatment with etelcalcetide is superior to treatment with cinacalcet as measured by the proportion of subjects with > 50% decrease in serum PTH from baseline, proportion of subjects with > 30% decrease in serum PTH from baseline, percent change from baseline in mean predialysis albumin corrected calcium (cCa) **measured by the central laboratory** and achievement of mean predialysis serum phosphorus (P) ≤ 4.5 mg/dL **measured by the central laboratory** during the efficacy assessment phase (EAP).

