4.1 Inclusion and Exclusion Criteria

4.1.1 Inclusion Criteria

- 101 Subject has provided informed consent prior to performing any study-related activities/procedures.
- 102 Male or female subjects \geq 18 years of age or older at the time of signing informed consent.
- 103 Subject must be receiving maintenance hemodialysis 3 times weekly for at least 3 months, with adequate hemodialysis with a delivered Kt/V \geq 1.2 or urea reduction ratio (URR) \geq 65% within 4 weeks prior to screening laboratory assessments. The Kt/V formula used for a subject must be the formula used during routine care prior to screening.

- 104 Dialysate calcium concentration must be ≥ 2.5 mEq/L (1.25 mmol/L) and stable for at least 4 weeks prior to screening laboratory assessments, and must remain ≥ 2.5 mEq/L (1.25 mmol/L) for the duration of the study.
- 105 Subject must have SHPT as defined by one central laboratory screening predialysis serum PTH value > 500 pg/mL (**53.00 pmol/L**), within 2 weeks prior to randomization.
- 106 Subject currently receiving vitamin D sterols must have had no more than a maximum dose change of 50% within the 4 weeks prior to screening laboratory assessments, remain stable through randomization, and be expected to maintain stable doses for the duration of the study, except for adjustments allowed per protocol or for safety reasons.
- 107 Subject must have 1 screening predialysis serum cCa laboratory value ≥ 8.3 mg/dL (**2.07 mmol/L**) measured within 2 weeks prior to randomization.
- 108 A subject receiving calcium supplements must have had no more than a maximum dose change of 50% within 2 weeks prior to screening laboratory assessments and remain stable through randomization.
- 109 A subject receiving phosphate binders must have had no more than a maximum dose change of 50% within the 2 weeks prior to screening laboratory assessments, remain stable through randomization, and be expected to maintain stable dose for the duration of the study, except for adjustments allowed per protocol or for safety reasons.

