10.5.3.1 Other Secondary Efficacy Endpoints

The following secondary endpoints will be formally tested if both key secondary endpoints are statistically significant. To control the family-wise error rate, the Hochberg procedure of adjustment for multiple comparisons will be used:

- percent change from baseline in mean predialysis **central laboratory** serum cCa during the EAP
- achievement of mean predialysis serum P \leq 4.5 mg/dL during the EAP

A repeated measures mixed effects model will be used to compare the percent change from baseline in serum cCa levels during the EAP, and will include the randomization stratification factors. The difference between treatment groups will be presented with 95% CI. The analysis will be performed on the FAS and **supplementary** analysis will be performed using the cCa completer analysis set. The achievement of mean predialysis serum P \leq 4.5 mg/dL during the EAP will be analyzed by using CMH test stratified by the randomization stratification factors. The difference between treatments will be estimated and presented with a 95% confidence interval. These analyses will be performed on the FAS using the nonresponder imputation for those subjects without laboratory values during the EAP.

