### 3. Study Overview

#### 3.1 Study Design

[figure not shown]
This is a phase 3, multicenter, randomized, active-controlled, double-blind, double-dummy, dose-titration, 26-week treatment period comparison of etelcalcetide and cinacalcet.

All subjects, regardless of treatment assignment, may receive standard of care as prescribed by the individual Investigator, with calcium supplements, phosphate binders, vitamin D sterols, and nutritional vitamin D supplements. If treatment with calcitriol or vitamin D analogs is ongoing when subjects are enrolled in the study, the doses of these agents should remain constant for the duration of study, unless treatment with vitamin D is initiated, interrupted, or adjusted for reasons of safety.

Subjects will be stratified by screening serum PTH level (< 900 pg/mL,  $\geq$  900 pg/mL), screening serum cCa (< 9.0 mg/dL,  $\geq$  9.0 mg/dL) measured by the central laboratory, and country (China and non-China), and be randomized 1:1 to receive etelcalcetide or cinacalcet.

The overall study design is described by a study schema in [Figure 3-1](#).

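### The test of mean P ≤ 4.5 mg/dL is valid but leaves out baseline phosphorus, which the trial already collects and could use at little cost

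*SAP*

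**What the plan says.** **Endpoint.** One of the two other secondary endpoints is "achievement of mean pre-dialysis serum P ≤ 4.5 mg/dL during the EAP" (SAP 9.5.2.2). It is a fixed threshold with no condition on the starting value. The primary, key secondary and calcium endpoints are all defined relative to baseline.

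**Test.** SAP 9.5.2.2 says the proportion "during the EAP will be analyzed using the CMH test stratified by the randomization stratification factors". Protocol 10.5.3.1 agrees: the endpoint "will be analyzed by using CMH test stratified by the randomization stratification factors". Those factors are screening PTH (cut at 900 pg/mL), screening cCa (cut at 9.0 mg/dL) and China versus non-China. The analysis uses the FAS, and subjects with no EAP value count as non-responders. It is reached only after both key secondary endpoints succeed, and is then tested with the calcium endpoint under Hochberg.

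**Entry.** Protocol 4.1.1 sets a PTH limit ("Subject must have SHPT as defined by one central laboratory screening predialysis serum PTH value" above 500 pg/mL) and a calcium limit ("Subject must have 1 screening predialysis serum cCa laboratory value" of at least 8.3 mg/dL). Protocol 4.1.2 names albumin, magnesium and transaminases. Neither section names phosphorus.

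**Baseline P.** It is defined: "Baseline values of PTH, cCa, and serum phosphorus are defined as the average of the last pre-dialysis assessment done during the screening period" and the Study Day 1 value (SAP 5.2). The schedule collects both, through the screening chemistry panel and the day 1 phosphorus sample. It is not among the ten covariates of SAP 4.1, so it is not a subgroup under SAP 4.2.

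**The concern.** With no entry limit on P, a subject who starts at 4.0 and ends at 4.4 mg/dL counts as achieving the target, although P rose. Subjects like this are expected equally in both arms, so the comparison is fair. The planned result still cannot show how much of the achievement rate is control gained and how much is control kept.

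The second issue is precision. Baseline P probably predicts EAP P. Protocol 6.5.6.2 recommends stable binder doses and allows adjustment after two consecutive local values above 5.5 or below 3.0 mg/dL, so many subjects may stay near where they began. Leaving out a prognostic baseline value can cost power, and it leaves the estimate open to chance imbalance in a factor that randomization does not balance.

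**Working it through.** **1. The plan's own figures.** The documents give no rate, effect size or power for the P endpoint. The nearest stated figures are in protocol 10.2 and SAP 3.2, and they reproduce. With n = 300 per arm and p̄ the mean of the two rates:

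Power = Φ{ [|p1 − p2| − 1.96·√(2p̄(1 − p̄)/n)] / √([p1(1 − p1) + p2(1 − p2)]/n) }

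- 52% vs 40%: (0.12 − 1.96 × 0.0407)/0.0404 = 0.996, so 84.0% (stated: about 84%).
- 68% vs 58%: 71.9% (stated: about 72%).
- Non-inferiority, margin 12%: above 99% (stated: over 99%).

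Everything below rests on assumed P distributions.

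**2. Where baseline P is used.**

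| Place | Baseline P used? |
|---|---|
| Entry criteria (protocol 4.1.1, 4.1.2) | No |
| CMH strata (SAP 9.5.2.2, protocol 10.5.3.1) | No |
| Covariates and subgroups (SAP 4.1, 4.2) | No |
| Baseline table (SAP 9.4) | Yes, descriptive |
| By-visit change from baseline, shift by toxicity grade (SAP 9.6.3) | Yes, descriptive |

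The descriptive items show imbalance and movement in P. None is set up to give the proportion reaching 4.5 mg/dL among subjects above it at entry.

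**3. Share of control-arm achievers already at target.** Let q be the share at or below 4.5 at baseline, a the control response among them, and b the control response among the rest. The share is qa/[qa + (1 − q)b]. With b = 20%:

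- q = 10%, a = 60%: 0.06/(0.06 + 0.18) = 25%.
- q = 40%, a = 75%: 0.30/(0.30 + 0.12) = 71%.

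A second model, with correlated baseline and EAP values, q of 15 to 35% and correlation r of 0.3 to 0.7, gives 26 to 63%.

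**4. Power without and with a baseline P stratum.** Both models take 330 per arm, 10% missing counted as non-response, and two-sided 5%.

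*Correlation model* (true difference 10 points, q = 25%, 8 strata versus 16, 6,000 simulated trials):

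| r | Without | With | Gain |
|---|---|---|---|
| 0.3 | 70.2% | 71.1% | +0.9 |
| 0.5 | 70.8% | 73.6% | +2.8 |
| 0.7 | 69.5% | 77.2% | +7.7 |

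The simulation error of each figure is about √(0.7 × 0.3/6000) = 0.6 points, so the gain at r = 0.3 is close to noise. Over q of 15 to 35% the gain runs from 0 to +9 points.

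*Response model* (b = 20%, common odds ratio 1.6, randomization factors not modelled, 40,000 simulated trials):

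| a | q | Without | With | Gain |
|---|---|---|---|---|
| 60% | 10% | 64.2% | 67.2% | +3.0 |
| 60% | 40% | 61.4% | 68.2% | +6.8 |
| 75% | 10% | 60.2% | 65.4% | +5.2 |
| 75% | 40% | 49.3% | 59.9% | +10.6 |

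**5. Type I error.** With no treatment effect both tests reject at 5.1% in the correlation model (q = 25%, r = 0.5), and at 4.8 to 5.2% in the response model.

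**6. Chance imbalance.** With q = 25%, the SD of the between-arm difference in the share at target is √(2 × 0.25 × 0.75/330) = 3.4 points. With a = 60% and b = 20%, a 2-SD imbalance moves the crude difference by about 6.7 × 0.40 = 2.7 points, or 2.4 after the 10% missing (2.7 × 0.9).

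**The case against.** The strongest reply is that nothing here is wrong. Randomization is 1:1, the test is stratified by the design factors, and type I error holds. The objective in protocol 1.2 is itself achievement of P ≤ 4.5 mg/dL during the EAP, so the endpoint measures what was asked. A reader might infer that counting subjects already at target biases the comparison, or that the endpoint misses its objective. The documents support neither inference: no text requires a start above 4.5 or calls the endpoint an improvement.

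The stakes are also low. The endpoint comes last in the hierarchy, behind a superiority test with a stated power of about 72%, and the sample size section claims no power for it. The summaries in SAP 9.4 and 9.6.3 already show baseline balance and change in P. The exploratory endpoints are not visible in the public text, so further P analyses cannot be ruled out. The prognostic strength of baseline P is a reasonable expectation, not a figure from the documents, and binder adjustments could weaken it.

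All of this stands. It limits the point to an optional gain in precision and reporting, but it does not remove it: a prognostic value that is already collected is absent from a formally tested analysis, and the descriptive summaries do not fill that gap.

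**Conclusion.** The planned test is valid and answers the stated objective. It omits a collected baseline value that probably predicts the outcome, and no analysis in the public text separates reaching the target from keeping it. Taking the two models together, adding the stratum gains about 0 to 10 points of power, with one model's top end just under 11. The gain is near zero if baseline and EAP P correlate weakly and about 2 to 3 points at r = 0.5. Type I error does not change.

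The textual facts are firm. The sizes are not: they rest on assumed shares at target, response rates and correlations, and none should be read as an estimate for this trial. The primary and key secondary conclusions are unaffected.

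**What to change.** As an optional improvement, made before unblinding in SAP 9.5.2.2 (and protocol 10.5.3.1 if it is amended):

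- Add baseline P (≤ 4.5 versus > 4.5 mg/dL) as a further stratum in both the CMH test and the estimate of the difference.
- Use the SAP 5.2 baseline definition. If the screening or the day 1 value is missing, use the one that is available. SAP 5.2 gives no rule for this case.
- Report descriptively, by arm, the proportion with EAP mean P ≤ 4.5 within each baseline category. This table is needed as well, because the stratum alone does not separate control gained from control kept.

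**Cost.** SAP wording and one table, with no new data. The strata rise from 8 to 16, averaging 660/16 ≈ 41 subjects. Some will be sparse: if 15% start at target, that is 99 subjects over 8 strata and 2 arms, about 6 per cell if spread evenly. CMH tolerates this, but the SAP should acknowledge it.
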